14.1.6 Adverse Events Related to immunosuppressant therapy

Adverse events that are related to corticosteroid or non-steroidal immunosuppressant will be summarized by SOC, PT and severity. In addition, a list of subjects with the AEs related to immunosuppressant therapy will be provided.

14.2 Clinical Laboratory Tests

Clinical laboratory tests include blood chemistry, hematology, urine tests, and coagulation. Clinical laboratory test values and change from Baseline will be summarized descriptively by visit. Shift tables cross-tabulating CTCAE v4.03 grade at Baseline vs. worst CTCAE v4.03 grade at post-Baseline visits will be provided as well. A supportive listing of abnormal test values with CTCAE v4.03 grade 3 or greater will be produced.

Liver tests (LTs) by central labs will be assessed on a regular basis, as detailed in the protocol. Boxplots of maximum ALT values at 4-week intervals over time and corresponding line plots will be provided. The same analyses based on mean or median ALT values will be conducted. ALT values and change from Baseline over time will be summarized descriptively. Summaries of ALT elevations including baseline ALT, time from infusion to ALT > ULN, ALT > 3x ULN, ALT > 5x ULN, ALT \geq 1.5x ULN or (> ULN & > 2x baseline value), ALT > 2x baseline value, ALT > 1.5x baseline value, ALT > 1.5x baseline value or > ULN, ALT > 2x baseline value or > ULN, peak ALT level, and duration of ALT elevation will be provided. Correlation of ALT elevation to FVIII levels, as well correlation of steroid treatment to ALT elevation and FVIII levels will be presented in subjects' profile figures. Correlation of alternative immunosuppressant (AIS) treatment to ALT elevation including time to ALT elevation recovery after AIS onset will be summarized. Local ALT assessments will be analyzed similarly as the central ALT assessments, if needed. Similar analyses will be applied to other liver tests including aspartate transaminase (AST), gamma-glutamyl transferase (GGT), lactate dehydrogenase (LDH), bilirubin, and alkaline phosphatase (ALP), if needed.

In addition, incidences of potential drug-induced liver injury (DILI) that include an elevated ALT or AST in combination with either an elevated bilirubin or clinical jaundice, as defined by Hy's law, will be summarized by count and percentage. The profile summary of the related laboratory tests results needed for determination by Hy's law will be provided for the subjects with potential DILI.

Finally, the impact of select concomitant medication use (e.g., lamivudine) on ALT elevations will be assessed in the same manner as outlined in Section 13.3.7 in the mITT subjects who have discontinued them before the data cut-off date for the 2-year analysis.

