11 PRIOR AND CONCOMITANT MEDICATIONS/PROCEDURES

Prior and concomitant medications are defined as follows:

- prior medication—any medication taken prior to the initiation of the investigational product and within 30 days prior to screening;
- concomitant medication—any medication taken after the initiation of the investigational product.

When a medication starts prior to the initiation of the investigational product and continues while on study, it will be summarized as both a prior and concomitant medication.

All medications will be coded using the current version of the World Health Organization Drug (WHO Drug) Dictionary.

Prior and concomitant medication use will be separately summarized by Anatomical Therapeutic Chemical (ATC) medication class (Level 4) and preferred name (i.e., generic medication name), and by NIH hepatotoxicity likelihood grades and preferred name as well. A subject reporting the same medication more than once will be counted once when calculating the number and percentage of subjects who received that medication.

Corticosteroid usage including total dose and total duration per subject, dose per corticosteroid course, duration per corticosteroid course, and time to corticosteroid course(s), and number of corticosteroid courses will be summarized for therapeutic purposes. Non-steroidal immunosuppressants may be summarized as well.

Baseline FVIII prophylaxis treatment will be summarized by type (extended half-life, standard half-life, and plasma derived) and drug preferred name.

Subjects who resume prophylactic treatment post BMN 270 infusion will be listed separately.

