13.3.6 FVIII activity and ABR in immunosuppression-free periods

To investigate potential confounding effects of immunosuppressant use on the treatment effect of BMN 270, FVIII activity and ABR in immunosuppression-free periods will be assessed for study 270-902 rollover subjects. The immunosuppression-free period is defined as the efficacy evaluation period for subjects who never received immunosuppressants (i.e., systemic corticosteroids or alternative immunosuppressants) and the efficacy evaluation period after the immunosuppressant has been discontinued for subjects who did receive immunosuppressants. The efficacy evaluation period starting from the first date of immunosuppressant use through the last date of immunosuppressant use is considered as the immunosuppression period. For subjects who received and then discontinued immunosuppressants, their ABR in the immunosuppression-free period will be compared to their ABR in the immunosuppression period. This comparison will be repeated for subjects whose immunosuppression-free period is at least one year vs. less than one year. The number of subjects who were off immunosuppressants at various timepoints (e.g. 3, 6, 9, 12, 18, 24 months, etc.) and the corresponding ABR will also be summarized.

For comparison purposes, FVIII activity levels over time and ABR in the efficacy evaluation period will be summarized for subjects who never received immunosuppressants and subjects who were still on immunosuppressants at the time of the data cut-off for the analysis.

13.3.7 Impact of cessation of immunosuppressant or select concomitant medication use on FVIII expression

The impact of cessation of immunosuppressant use on FVIII expression will be evaluated in the mITT subjects who have discontinued immunosuppressant therapy before the data cut-off date for the 2-year analysis. To account for time factor, subjects will be divided into

Study 270-301 Statistical Analysis Plan

subgroups based on their timing of immunosuppressant discontinuation (Weeks 14-26, 27-39, 40-52, et al.). Each subject's median FVIII activity level in the 4 weeks immediately after immunosuppressant discontinuation will be compared to that immediately prior. The median change in FVIII activity will be plotted against the median time to immunosuppressant discontinuation in each of the subgroups.

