For comparison purposes, similar analyses will be performed to assess the natural decline of FVIII activity while subjects are on or off immunosuppressants. Changes in FVIII activity levels between 4 weeks before and 4 weeks after Week 20, 24, 28, et al. will be plotted separately for subjects who ever or never received immunosuppressant therapy.

The above analyses will be repeated for select concomitant medications (e.g., lamivudine) to assess the impact of such on FVIII expression in the mITT subjects who have discontinued them before the data cut-off date for the 2-year analysis.

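### The before/after-stopping analysis of concomitant medication and ALT does not separate stops that follow an ALT rise, so the rise's own course can appear as a drug effect

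*SAP*

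**What the plan says.** SAP Section 14.2 defines the ALT analysis only by cross-reference: "the impact of select concomitant medication use (e.g., lamivudine) on ALT elevations will be assessed in the same manner as outlined in Section 13.3.7". The analysis set is stated as "in the mITT subjects who have discontinued them before the data cut-off date for the 2-year analysis". No condition is placed on why the drug was stopped.

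Section 13.3.7 supplies the method. Each subject's "median FVIII activity level in the 4 weeks immediately after immunosuppressant discontinuation will be compared to that immediately prior". Subjects are grouped by the calendar timing of the stop, and the median change is plotted against the median time to stopping. A reference series, intended to show how FVIII falls over time without regard to a stop, is also planned: "Changes in FVIII activity levels between 4 weeks before and 4 weeks after Week 20, 24, 28, et al. will be plotted separately", by ever or never use of immunosuppressants. The section then says that these analyses are repeated for select concomitant medications.

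Other relevant places:
- Section 11 summarises all medications "by NIH hepatotoxicity likelihood grades and preferred name as well".
- The Note to File refers to systemic immunosuppression indicated for ALT elevation.
- Section 14.2 plans a summary of time to ALT recovery after the start of alternative immunosuppressants.
- The synopsis calls the concomitant-medication assessments descriptive, and Section 14 plans no formal safety testing.

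**The concern.** A before/after-stopping contrast is interpretable when the stop date is unrelated to the outcome's recent path. An ALT rise, however, is a plausible reason to stop a drug suspected of liver toxicity, and then the outcome sets the date around which the windows are placed. The before window holds part of the rise. The after window holds the rest of its course, together with the response to any immunosuppressant given for it. None of that is due to the concomitant drug.

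The stated aim is the drug's impact on ALT elevations, which is a question of cause. If a material share of stops followed an ALT rise, an inert drug could look harmful because ALT falls after stopping. A harmful one could look harmless because ALT was still climbing when it was stopped.

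**Working it through.** The SAP gives no figure to reproduce. The check has three parts: what the plan conditions on, one worked episode, and simulations of a drug with no effect.

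**What the plan conditions on.** The contrast is stratified by calendar time of the stop only. The reference is centred on fixed weeks and was designed to show FVIII decline. Neither uses the reason for stopping, ALT at the stop, or immunosuppressant changes near the stop. Two details are left open. The four-week length is explicit for the after window and for the reference series, but not for the before window of the main contrast. Use of the median for ALT is inferred from the cross-reference. Four-week windows and medians are assumed below.

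**One noise-free episode.** Assumptions, none from the SAP: normal ALT 25 U/L, peak three times normal, linear rise over 3 weeks, excess halving every 2 weeks, weekly values, no drug effect. After the peak, ALT at week k is 25 × (1 + 2 × 0.5^(k/2)). From 4 weeks before to 6 weeks after the peak, the values are 25, 25, 41.7, 58.3, 75, 60.4, 50, 42.7, 37.5, 33.8, 31.3.

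The contrast is the median of the 4 values after the stop minus the median of the 4 values up to and including the stop.

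| Stop | Median before | Median after | Change |
|---|---|---|---|
| 1 week before peak | (25 + 41.7)/2 = 33.3 | (50 + 60.4)/2 = 55.2 | +21.9 U/L (+66%) |
| At peak | (41.7 + 58.3)/2 = 50.0 | (42.7 + 50)/2 = 46.3 | -3.7 U/L (-7%) |
| 2 weeks after peak | (58.3 + 60.4)/2 = 59.3 | (33.8 + 37.5)/2 = 35.7 | -23.7 U/L (-40%) |

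The same rise gives a change of either sign according to the stop date alone. The windows in Appendix 20.1 put liver tests weekly to Week 36, every 2 weeks to Week 52, and every 4 weeks to Week 104. After Week 52 a four-week window therefore holds about one scheduled value, and the median smooths nothing. The peak against the value 4 weeks later, 75 against 37.5, would be -50%.

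**Simulation A, inert drug, mixed reasons for stopping.** Assumptions: 4,000 subjects per scenario; normal ALT 25 U/L (between-subject log SD 0.25, weekly log SD 0.15); one rise each to 2-4 times normal, with a 3-week upslope and a half-life of 1, 2 or 4 weeks; prompted stops 0-2 weeks after the peak; other stops at random. Median change in U/L, mean in brackets:

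| Half-life | 0% prompted | 25% | 50% | 100% |
|---|---|---|---|---|
| 1 week | -0.1 (-0.1) | -1.7 (-6.0) | -7.4 (-11.3) | -20.6 (-22.6) |
| 2 weeks | -0.2 (0.0) | -1.4 (-4.3) | -3.7 (-8.1) | -14.8 (-15.8) |
| 4 weeks | -0.5 (0.0) | -1.1 (-1.5) | -2.1 (-3.3) | -6.5 (-6.1) |

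The fixed-week reference stayed at 0.0 to -0.6 (median) and -0.1 to +0.1 (mean) in every scenario, so it neither reveals nor removes the artefact. All prompted stops here come at or after the peak, so only falls can appear.

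**Simulation B, inert drug, stop 1-6 weeks after the first ALT above 43 U/L.** Assumptions: weekly ALT, baseline about 25 U/L, episodes of 1.5-3 times baseline lasting 3-8 weeks, within-subject log SD 0.2-0.3. Median relative change:
- no prompted stops: -0.1% to +1.6%
- 10% prompted: -4% to +2%
- 25% prompted: -10% to +5%
- all prompted: +40% to +67% at 1 week, 0 to +8% at 2 weeks, about -18% to -19% at 3 weeks, -24% to -33% at 4-6 weeks.

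A further run of the same kind gave about -8% to +7% at 25% prompted and -37% to +61% at 100%.

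**The case against.** The strongest reply is that the plan claims little here. The analysis is descriptive, with no test, threshold or decision rule, and it touches no efficacy endpoint. This stands: the most that can be said is that the rise's course can be read as a drug effect. A reader might infer that the plan will read it so, but no text says that.

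Second, the SAP does not state that any select medication was stopped because of ALT. A reader might take the hepatotoxicity grading in Section 11 as evidence. It is a summary of all prior and concomitant medications; it does not define the select ones or give reasons for stopping. The size therefore depends on an unknown share, and at 10% to 25% prompted the median change is modest.

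Third, a reader might infer that the analysis could shift ALT elevations away from BMN 270. The SAP does not support this. ALT thresholds, peak, duration and potential Hy's law cases, the ALT event of interest, and investigator-assessed relatedness are all reported separately in Sections 14.1 and 14.2.

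Fourth, when the analyses are repeated for a medication, the fixed-week reference may become ever versus never users of that medication and so include continuers. Section 14.2's restriction to subjects who stopped leaves this unclear. On either reading the reference is not matched on ALT, so it does not answer the point.

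**Conclusion.** The point holds as a gap in specification. Section 14.2 applies a stop-anchored contrast to an outcome that can itself prompt the stop, and nothing in the plan separates or matches for that. With no prompted stops the artefact is negligible. At 25% prompted it is roughly -10% to +5% in the median, and it is large, with either sign, only if most stops were prompted. These sizes rest on assumed ALT episodes and assumed shares of prompted stops, since the SAP supplies neither. The consequence is a possibly misleading safety interpretation; type I error is not involved.

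It does not follow that conclusions should be drawn only from stops preceded by normal ALT. That conditions on the outcome. In a simulation of a truly hepatotoxic drug (ALT raised 2.5 times in 20-40% of users, stops unrelated to ALT), the planned contrast showed a median fall of 7-25%. The subset with ALT at or below the upper limit of normal before the stop kept only about 1% to 2% of affected users and showed no fall.

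**What to change.** In Section 14.2, replace the bare cross-reference with an ALT-specific description:

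- State the before window and the ALT summary used.
- Present the change separately for (a) stops with no ALT elevation recorded as the reason and no immunosuppressant start or dose change in the window, and (b) stops during or after an ALT rise, or with an immunosuppressant change in the window.
- Define (a) by recorded reason and immunosuppressant dates where available, not only by ALT at or below the upper limit of normal. Do not restrict conclusions to subjects with normal ALT before the stop, since that removes any drug-caused elevation.
- Show (b) beside ALT episodes of similar height and time since infusion in subjects who continued the drug or never used it.
- Add the rate of new ALT elevations on versus off the drug in all users, stratified by time since infusion and shown beside never-users over the same weeks. A crude on/off rate would be confounded by time since infusion.

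The cost is SAP wording and modest programming on existing ALT, medication and immunosuppressant dates, with small subgroups as the downside. The Note to File records that the 2-year analysis was run in January 2022, so for those data this would be a supplementary analysis labelled as such.

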14.3 Vital Signs and Physical Examination

Vital signs variables include systolic blood pressure, diastolic blood pressure, heart rate, respiration rate, and temperature. Vital signs will be summarized descriptively by visit. Physical examinations will include assessments of general appearance; head, eyes, ears, nose, and throat; the cardiovascular, dermatologic, lymphatic, respiratory, gastrointestinal, genitourinary, musculoskeletal, and neurologic systems. Physical examination results (normal or abnormal) will be summarized descriptively by visit.

14.4 Electrocardiogram, Chest X-Ray and Liver Ultrasound

Electrocardiogram (ECG), chest X-ray and liver ultrasound are performed at the Screening visit with additional evaluations to be performed if clinically indicated during the study. Test results (normal, abnormal, or unknown) will be summarized or provided in data listings, as appropriate for the amount of data collected.

14.5 Viral Shedding

Viral shedding will be extensively studied at Baseline, Day 4, Day 8, Week 2, Week 3, Week 4, Week 6, Week 8, Week 12, Week 16, Week 20, Week 24, Week 26, and every 4 weeks between Weeks 32-52 until at least 3 consecutive negative results are obtained. Body fluids including blood, saliva, semen, urine and stool will be tested by polymerase chain reaction (PCR) at these time points. Testing of semen will continue at least through Week 12, even if 3 consecutive negative results have been recorded in that compartment prior to that time point. Subjects who have not had 3 consecutive negative semen samples by Week 52 should continue to have PCR testing in semen every 4 weeks (during Year 2) or every 6 weeks (during Years 3-5) until 3 consecutive negative samples are documented (or upon consultation between the Investigator and Medical Monitor).

The vector genomes tested in extracted body samples will be summarized by visit with descriptive statistics and in graphical format. In addition, the number (%) of patients with detectable vector genomes by visit and sample type, the duration of shedding by sample type, and the peak period(s) of shedding by sample type will be summarized. Values below the LLoQ will be imputed as one half of the validated LLoQ of 50 vg/q PCR and back calculated to the theoretically corresponding genome amounts per standard unit of biospecimen.

15 IMMUNOGENICITY ASSESSMENT

Analysis of immunological parameters will be primarily descriptive. Assays to detect pre-existing immunogenicity specific for AAV5, including plasma derived inhibitors of transduction (transduction inhibition or TI) and total antibody (TAb) assays, will be tested at the Screening visit before BMN 270 infusion is given and at post-baseline visits according to the protocol's schedule of events. Test results (negative and positive with titer) will be summarized and provided in data listings, as appropriate for the amount of data collected.

Two assays are in place to determine immunogenicity to the human FVIII transgene product. The first is a total antibody (TAb) assay to detect binding antibodies in patient plasma directed against human FVIII and is reported as negative or positive with titer. The second is to evaluate neutralizing antibodies (NAb) capable of interfering with FVIII activity (FVIII Inhibitors) and is determined using the Bethesda assay with Nijmegen modification. This assay is reported out in Bethesda Units (BU), with a value of <0.6 considered negative. Both assays will be performed on patient plasma samples obtained at the screening visit, and at post-baseline visits according to the protocol's schedule of events. Test results will be summarized and provided in data listings as appropriate for the amount of data collected. The associations between antibody responses and the occurrence of adverse events or other safety or efficacy endpoints, such as FVIII activity values and clinical chemistries, may be explored.

Cellular immunity in the form of cytotoxic T lymphocytes (CTL) will be evaluated by Interferon-gamma (IFN- γ) ELISpot assay of peripheral blood mononuclear cells (PBMC). PBMC will be stimulated with overlapping peptide pools derived from the AAV5 capsid protein or human FVIII protein sequences to evaluate IFN- γ secretion by CTL targeting both the AAV5 capsid and the FVIII transgene product. Cellular immunity will be evaluated at baseline and at post-infusion visits according to the protocol's schedule of events and is reported positive or negative by peptide pool stimulation and as spot forming units (SFU) per 10^6 PBMC. Test results will be summarized and data listings will be generated reporting positive or negative and the number of SFU 10^6 PBMC for each peptide pool and control stimulation for each patient at each study visit tested. Positive and negative results with the number of SFU per 10^6 PBMC will be evaluated for correlations with FVIII activity measures, changes in clinical chemistry or adverse events as appropriate for the data collected.

Study 270-301 Statistical Analysis Plan

16 CLINICAL PHARMACOLOGY

Clinical pharmacology analyses will be specified in a separate clinical pharmacology analysis plan.

**Study 270-301 Statistical Analysis Plan****17 OTHER ANALYSIS**

Study 270-301 was ongoing during the COVID-19 pandemic and remained ongoing despite the disruption that occurred. The study was fully enrolled with all subjects in post-dosing follow-up when the pandemic was declared and therefore had no impact on study sample size. However, pandemic did affect the study conduct.

Additional analyses will be conducted as appropriate to evaluate the impact of the COVID-19 pandemic on the study conduct and results, especially for the treatment effect as estimated in the trial. Summaries of study participation with missing visits, study disposition and protocol deviations due to COVID-19 pandemic will be provided. Safety and efficacy endpoint result changes relative to timing of COVID-19 pandemic will be summarized.

19 SUMMARY OF CHANGES TO TWO-YEAR ANALYSIS SAP

Table 19.1 provides summary of revisions across versions of SAP.

Table 19.1: Summary of Revisions

Version		Affected Section(s)	Summary of Revisions
Number	Date		
1.0	16JUL2021		Initial version
2.0	13DEC2021	Multiple	Addressed FDA SAP comments (Request for Information Oct 2021): 
 • Added a 5th- 9th hypothesis testing for superiority in ABR for all bleeds and Haemo-QoL-A endpoints (Total Score, Physical Functioning, Consequences of Bleeding, Role Functioning) • An alpha level of 0.05 was specified for the two-year analyses • The Efficacy Evaluation Period (EEP) for the primary analysis of ABR, annualized FVIII utilizations and annualized FVIII infusions was changed from Week 5 to last visit by data cut-off to Post FVIII prophylaxis to last visit by data cut-off. • Primary estimand was clarified • Added a summary of the subjects off immunosuppressants at various timepoints and the corresponding ABR • Additional NI tests for ABR (treated bleeds) using smaller margins were removed • Clarified the purpose of pre-specifying an imputation method for missing ABR data

	Study 270-301 Statistical Analysis Plan
---	--

